8.1. Adverse Event Definition

An AE is any untoward medical occurrence associated with the use of a drug, whether or not considered drug related. An AE can be any unfavourable and unintended sign (including an abnormal laboratory finding), symptom, or disease temporally associated with the use of the study drug, whether or not it is considered to be study drug related. This includes any newly occurring event or previous condition that has increased in severity or frequency since the administration of study drug.

8.2. Adverse Drug Reaction Definition

An ADR is an AE suspected to be causally related to a product. In clinical studies this means that the investigator has judged that there is at least a reasonable possibility that the event is related to the product.

8.3. Serious Adverse Event Definition

A SAE is any AE, occurring at any dose and regardless of causality defined as;

- death
- a life-threatening AE (means that the patient was at immediate risk of death as it occurred, does not include if the death may have occurred if a more severe form)
- in-patient hospitalisation or prolongation of existing hospitalisation

- a persistent or significant incapacity or substantial disruption of the ability to conduct normal life functions
- a congenital anomaly or birth defect
- regarded as medically important without meeting the above mentioned criteria

8.4. Adverse Events by Intensity

Intensity for each AE, including any laboratory abnormality, will be defined according to the following criteria:

MILD: An event that is easily tolerated by the patient, causing minimal discomfort and not interfering with everyday activities.

MODERATE: An event that is sufficiently discomforting to interfere with normal everyday activities.
--

SEVERE: An event that prevents normal everyday activities.

When changes in the intensity of an AE occur more frequently than once a day, the maximum intensity for the experience should be noted. If the intensity category changes over a number of days, then those changes should be recorded separately (with distinct onset dates).

8.5. Classification of Adverse Events by Relationship to Study Drug

UNLIKELY RELATED: This category applies to those AEs that are judged to be unrelated to the test drug.

LIKELY RELATED: This category applies to those AEs that the investigator feels are with high probability related to the test drug.

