8.6. Reporting of Adverse Events

At each visit, the patient will be asked if any new signs or a symptom has occurred since last visit. For all AEs, the investigator must obtain information to determine the outcome of the AE and to assess whether it meets the criteria for classification as a SAE.

All AEs, serious and non-serious, should be recorded in the eCRFs. If no AE has occurred during the study period, this should also be recorded in the eCRF.

Preferably all AEs should be recorded in standard medical terminology rather than the patient's own word; if possible diagnosis instead of symptoms should be recorded.

UC is associated with certain characteristic signs and symptoms including diarrhea and rectal bleeding that may be present at Screening Visit and may fluctuate based on individual patient's disease history during the course of the study. These signs and symptoms are considered medically anticipated clinical events for the condition under study and will not be collected as an AE. These characteristics of disease activity will be regularly captured.

Exacerbations of disease activity (increase in the daily amount of rectal bleeding beyond the patient's normal fluctuation, new signs or symptoms of UC) will be collected as AEs and reported according to regulatory reporting requirements.

The following evaluations are to be done by the Investigator in connection with the AE:

- type of event
- seriousness
- degree of severity
- duration (start - end)
- action taken
- causality with study product
- outcome of the AE

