8.7. Reporting of Serious Adverse Events

All SAEs must be reported to the [REDACTED] Drug Safety Services within 24 hours by the Investigator or delegate, regardless of the time that may have elapsed from the time the event occurred to when the Investigator first learns of it. The initial report should contain as a minimum the following information:

- patient identification
- treatment specification
- AE diagnosis
- time specification for the medical event
- name of the original reporter

Any new information regarding the SAE report should be reported within 24 hours of knowledge. Apart from the information above, this follow-up report should also contain the following information:

- assessment of severity
 - assessment of causality

SAEs should be reported to [REDACTED] Drug Safety Services even after the clinical study has been finished, if, in the judgment of the Investigator, there might be an association between the event and previous use of the study product, or as a result of the study procedures.

Only SAEs that are both unexpected and related to the study drug, Suspected Unexpected Serious Adverse Reactions (SUSARs), are subject to expedited reporting.

The Sponsor is responsible for informing all Investigators concerned of relevant information about SUSARs that could adversely affect the safety of patients. The appropriate ethics committee (EC) and regulatory authorities, as per local requirements, should be informed by the Sponsor about SAEs associated with the use of the product.

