9.7. Safety Analysis

9.7.1. Analysis of Adverse Events

The number and percentage of patients reporting AEs, and the number of AEs reported will be presented. The events will be tabulated by system organ class and preferred term. In addition, summaries by relationship to study drug and severity will be presented. SAEs will also be presented in separate tabulations.

The number of patients experiencing an AE will be compared descriptively between groups.

All patients with AEs will be listed individually with patient number in addition to type of event, start and stop time, duration, seriousness, severity, action taken, relationship to study drug and outcome of AE.

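### The two causality definitions in section 8.5 leave a gap, and the upper one is narrower than the ADR definition in section 8.2 (minor wording conflict)

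*Combined protocol and SAP*

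**What the plan says.** Section 8.6 lists the evaluations the investigator makes for each adverse event, among them "causality with study product". The protocol's only scale for that evaluation is in section 8.5, which has two categories:

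- Lower: "UNLIKELY RELATED: This category applies to those AEs that are judged to be unrelated to the test drug".
- Upper, labelled as likely related: "This category applies to those AEs that the investigator feels are with high probability related to the test drug".

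Section 8.2 defines an ADR as an event suspected of being caused by the product. For clinical studies it explains this to mean that "the investigator has judged that there is at least a reasonable possibility that the event is related to the product".

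Relatedness is then used in two further places. Section 9.7.1 states that "summaries by relationship to study drug and severity will be presented", and it also plans individual listings that show the relationship. Section 8.7 states: "Only SAEs that are both unexpected and related to the study drug, Suspected Unexpected Serious Adverse Reactions (SUSARs), are subject to expedited reporting". Nothing in the protocol links the 8.5 categories to the 8.2 definition, and 8.7 does not say which threshold its word for relatedness carries.

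**The concern.** A two-level causality scale is a legitimate choice, but it works only if every event has a place and the dividing line is known. Here the two definitions sit at opposite ends, with nothing between them. The label of the lower category (unlikely) also disagrees with its definition (unrelated). The upper definition asks for more certainty than the ADR definition three sections earlier.

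What is at stake is the meaning of the relationship tables. Safety and tolerability is a secondary objective of this dose-optimisation trial, and section 9.7.1 compares adverse events between groups descriptively only. About 90 sites are planned. If they resolve the gap in different ways, a count of related events would mean neither ADRs as defined in 8.2 nor events of high probability.

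**Working it through.** No arithmetic applies and there is no stated figure to reproduce. The check sets the definitions side by side.

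| Investigator's judgement | ADR under 8.2? | Place under the 8.5 definitions |
|---|---|---|
| Unrelated | No | Lower category |
| Remote, short of a reasonable possibility, but not ruled out | No | Neither definition; the label points to the lower category |
| Reasonable possibility, not high probability | Yes | Neither definition |
| High probability | Yes | Upper category |

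**Step 1: exhaustiveness.** An event judged reasonably possible has not been judged unrelated, so it fails the lower definition. If it is not highly probable, it fails the upper one too. The definitions are not exhaustive.

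**Step 2: nesting.** High probability implies at least a reasonable possibility, but the reverse does not hold. As worded, the upper category is a narrower set than the ADRs of 8.2.

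**Step 3: effect on a table by relationship.** Suppose m events fall in the third row and investigators put k of them in the upper box. The upper box then omits m − k events that 8.2 calls ADRs. That is 0 if all go up (k = m) and m if all go down (k = 0). The documents give neither m nor k, overall or by arm. No size, and no direction for a comparison between arms, can be derived.

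**Step 4: where the category is used.**

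- The section 9.7.1 summaries and listings by relationship depend on it.
- The all-causality AE and SAE tables do not.
- Initial SAE reporting does not: every SAE goes to "Drug Safety Services within 24 hours by the Investigator or delegate", whatever its causality.
- The primary efficacy test in section 9.5 does not refer to it.
- The expedited-reporting sentence in 8.7 depends on relatedness but names no threshold, so whether 8.5 governs it cannot be settled from the text.

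**The case against.** The strongest reply is that no planned analysis fails. ADRs are not among the safety endpoints in section 3.2.3, and 9.7.1 promises tables by relationship, which is what an 8.5 variable supplies. With two labelled boxes an investigator will tick one, so in practice the scale divides events in two. Every event is also listed individually, and the separate SAP announced in section 9.1 could define the grouping.

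Much of this stands, and it limits the consequence. It does not remove the conflict. Read by labels alone, the upper box still begins at likely, which is not a reasonable possibility. A SAP can regroup what was recorded. If the eCRF holds only these two boxes (an assumption, since the form is not in the documents), neither a table rule nor a listing can recover a distinction that was never captured.

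Three stronger readings are tempting and are not supported:

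- **Expedited reports will be missed.** Section 8.7 requires relatedness without a threshold and may well intend that of 8.2. The effect is undetermined.
- **The rest of section 8 shows that 8.5 is the odd one out.** The word for suspicion in the SUSAR sentence is part of the expanded term, while its operative condition is relatedness. The sentence on SAEs after the study, where "there might be an association between the event and previous use of the study product", triggers late reporting and does not classify events. Section 8.8 speaks of a potential causality having been established, which is not plainly a suspicion-level test. The conflict that can be shown is 8.2 against 8.5.
- **The tables will favour active treatment.** Causality is judged under the blinding of section 5.2, apart from any emergency unblinding under 5.5. Nothing in the documents points to one arm.

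**Conclusion.** The conflict in wording is real. As defined, the 8.5 categories are not exhaustive, and the upper one is narrower than the 8.2 definition of an ADR. Events between the two thresholds have no defined place, so they may be coded inconsistently and the descriptive outputs by relationship need not capture protocol-defined ADRs.

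The severity is minor. Confidence is high for the wording conflict only. Any practical consequence depends on how many events fall in the gap, how investigators place them, and what the eCRF guidance and the SAP say, none of which the documents give.

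**What to change.** Reword section 8.5 so that its categories cover every event and the line between related and not related is the protocol's own 8.2 threshold. The simplest form has two categories: *related*, where a causal link to study drug is at least reasonably possible, and *not related*, where it is not. A scale with more levels would also serve, provided the same line is marked on it. Match the eCRF label and completion guidance. State once that this boundary defines an ADR, the meaning of related in 8.7, and the grouping in the 9.7.1 relationship summaries.

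The cost is protocol wording and eCRF text. The two-category form needs no new data item. The downside is that somewhat more events may be classed as related, and possibly a few more reports expedited if sites had been applying the 8.5 wording.

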8.6. Reporting of Adverse Events

At each visit, the patient will be asked if any new signs or a symptom has occurred since last visit. For all AEs, the investigator must obtain information to determine the outcome of the AE and to assess whether it meets the criteria for classification as a SAE.

All AEs, serious and non-serious, should be recorded in the eCRFs. If no AE has occurred during the study period, this should also be recorded in the eCRF.

Preferably all AEs should be recorded in standard medical terminology rather than the patient's own word; if possible diagnosis instead of symptoms should be recorded.

UC is associated with certain characteristic signs and symptoms including diarrhea and rectal bleeding that may be present at Screening Visit and may fluctuate based on individual patient's disease history during the course of the study. These signs and symptoms are considered medically anticipated clinical events for the condition under study and will not be collected as an AE. These characteristics of disease activity will be regularly captured.

Exacerbations of disease activity (increase in the daily amount of rectal bleeding beyond the patient's normal fluctuation, new signs or symptoms of UC) will be collected as AEs and reported according to regulatory reporting requirements.

The following evaluations are to be done by the Investigator in connection with the AE:

- type of event
- seriousness
- degree of severity
- duration (start - end)
- action taken
- causality with study product
- outcome of the AE

8.7. Reporting of Serious Adverse Events

All SAEs must be reported to the [REDACTED] Drug Safety Services within 24 hours by the Investigator or delegate, regardless of the time that may have elapsed from the time the event occurred to when the Investigator first learns of it. The initial report should contain as a minimum the following information:

- patient identification
- treatment specification
- AE diagnosis
- time specification for the medical event
- name of the original reporter

Any new information regarding the SAE report should be reported within 24 hours of knowledge. Apart from the information above, this follow-up report should also contain the following information:

- assessment of severity
 - assessment of causality

SAEs should be reported to [REDACTED] Drug Safety Services even after the clinical study has been finished, if, in the judgment of the Investigator, there might be an association between the event and previous use of the study product, or as a result of the study procedures.

Only SAEs that are both unexpected and related to the study drug, Suspected Unexpected Serious Adverse Reactions (SUSARs), are subject to expedited reporting.

The Sponsor is responsible for informing all Investigators concerned of relevant information about SUSARs that could adversely affect the safety of patients. The appropriate ethics committee (EC) and regulatory authorities, as per local requirements, should be informed by the Sponsor about SAEs associated with the use of the product.

8.8. Follow-up Period after an Adverse Event

If a patient is to discontinue due to an AE, or if an SAE persists at the end of the study treatment period, this should be followed up until the condition has resolved or until the patient is under professional medical care and a potential causality between the study drug and the SAE has been established. An outcome assessment should be performed when an AE persists.

In case of pregnancy during the study the patient and offspring must be monitored for AEs during the entire pregnancy. Any AE occurring to the offspring during pregnancy or at birth must be reported. The pregnancy should be reported in eCRF as an AE and also reported to [REDACTED] via Pregnancy report form.

8.9. Coding of Adverse Events

All AEs will be coded according to medical dictionary for regulatory activities (MedDRA) by [REDACTED] after the eCRFs have been collected from the study centres.

9. STATISTICAL CONSIDERATIONS

9.1. Statistical Analysis Plan

The principal features of the statistical analysis of the data are described in this section. A more technical and detailed elaboration of the principal features will be written in a separate Statistical Analysis Plan (SAP). A data display plan (DDP) will also be prepared and included in the SAP. The DDP will describe the layout of the tables and listings to be produced.

9.3. Study Population

9.3.1. Full Analysis Set

The full analysis set (FAS), will be based on the intention-to-treat (ITT) principles, which consists of all randomised patients who meet the inclusion criteria (as assessed by the investigator on the inclusion/exclusion criteria form), and receive at least one dose of the study drug (active or placebo).

9.3.2. Per Protocol Set

The per protocol set (PPS) is defined as FAS patients who do not have important protocol deviations considered to have a major effect on the primary efficacy endpoint, and have completed the Modified Mayo score (excluding friability) assessment at Week 0 and Week 6.

Patients in the PPS are analysed according to their randomised treatment.

9.3.3. Safety Analysis Set

The Safety Analysis Set is defined as all patients randomised in the study and treated with at least one dose of any study drug, i.e. cobitolimod in any dose or Placebo. Safety Analysis Set patients are analysed according to their actual treatment received.

9.4. Patient Demographic and Baseline Characteristics

Baseline values and patient characteristics will be presented in tables by group and in total.

All continuous variables will be described using standard statistical measures, i.e., number of observations, mean and median value, standard deviation, minimum and maximum value. All categorical variables will be summarised in frequency tables.

9.5. Primary Efficacy Endpoint Analysis

Sub scores of blood in stool, stool frequency will be based on the data collected in the eDiary. The measure of stool frequency will be derived calculating the mean daily stool frequency. The measure of blood in stool will be derived calculating the maximum (worst) outcome. Both measures will be derived using the most recent three consecutive days prior to the Week 0 and Week 6 visit, excluding the last two days before these visits.

The rationale for the exclusion of the last two days before the endoscopic procedure is that the preparation for the endoscopy can interfere with the natural clinical course of the symptoms.

A complete description of the derivation rules for the primary endpoint will be described in the SAP.

The analysis of the primary endpoint is conducted on the FAS and PPS.

The primary analysis of the primary endpoint will be performed using the Cochran Mantel Haenzel test adjusting for randomisation strata GCS use/non use and TNF- α prior use/non use at Baseline, Week 0.

The primary endpoint will be proportion of patients with clinical remission at Week 6 tested using an overall type I error rate of 0.10, using a one sided test.

The p-value for testing the null hypotheses must be less than 0.10 to be considered to have met the primary objective.

The primary efficacy endpoint will also be tested using the same approach as described above but with the use of an overall type I error rate of 0.05 using a two-sided test.

There will be no adjustment for multiplicity as all results will be regarded as exploratory. If a statistically significant difference among cobitolimod groups compared to placebo will exist, an analysis in terms of fractional polynomial for analysis of binary data will be applied to explore the dose-response relationship [23].

9.6. Exploratory Efficacy Endpoints Analyses

No multiplicity adjustments are made computing p-values of tests on exploratory variables; reported p-values are nominal. For overall comparison among more than two groups, the null hypothesis is that the proportions are the same in all groups.

The same analysis approach used for the primary efficacy endpoint will be applied to the exploratory efficacy variables referred to as a “Proportion endpoints”.

Continuous endpoints such as mean change from baseline will be evaluated using the ANCOVA, including treatment and stratifying factors as fixed factors and baseline as a covariate in the model.

